18.3.2 Safety Variables

The first usable assessment at the Withdrawal Visit for safety variables (laboratory tests, vital signs, weight and ECGs) will be assigned to a nominal visit in the corresponding Treatment Period, according to the visit windowing specified in Panel 11.

For assessments at the Baseline II/III Visit, the last usable assessment will be used. For assessments at visits post-baseline, the first usable assessment from the scheduled visit will be used, or the assessment from the Withdrawal Visit will be used if no scheduled assessment is available.

LU Study Number: 14861B Trial Site Number: Study Level Pluto ID: CLI 00933680

Panel 11 Visit Windows for Safety Assessments

Nominal Visit Number	Nominal Visit Week	Nominal Visit Day	Time Window
Open-label treatment period			
V1 (Baseline II/Completion Visit for lead-in study)	0	0	0
V2	4	28	1 to 41
V3	8	56	42 to 69
V4	12	84	70 to 111
V5	20	140	112 to 167
V6 (Completion Visit for open-label treatment period)	28	196	>167
Open-label treatment period with memantine (APTS2)			
V6 (Baseline III/Completion Visit open-label treatment period)	28	196	167 to 209
V8	32	224	210 to 237
V9	36	252	238 to 265
V10	40	280	266 to 321
V11 (Completion visit for open-label treatment period with memantine)	52	364	>321

18.4 Handling of Missing or Incomplete Dates/Times

18.4.1 IMP Start and Stop Dates

A missing IMP start date will be imputed with the date of Baseline II for patients in the APTS with an unknown IMP start date.

A missing IMP stop date will not be imputed. As such, exposure will be missing for a patient with a missing IMP stop date and the patient will contribute as having no exposure in the calculation of PYE. If it can be ascertained from other data that the patient did take IMP until a specific date, this date may be used to calculate exposure.

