6.2 Withdrawal

The number of patients who withdrew from the open-label treatment period will be summarised by primary reason for withdrawal as well as by all reasons for withdrawal.. Similar summaries will be created for the open-label treatment period with memantine. The summaries will also be presented by lead-in study for the open-label treatment period.

Patients who withdrew from treatment during the open-label treatment period will be listed and the listing will include the number of days on idalopirdine in the open-label treatment period, the primary reason for withdrawal from treatment, and all reasons for withdrawal from treatment. A similar listing will be created for patients who withdrew from treatment during the open-label treatment period with memantine.

7 Demographics and Other Baseline Characteristics

Demographics and baseline characteristics at Baseline I will be summarised for patients in the APTS and the APTS2.

Demographics (sex, age, ethnicity, and race), patient characteristics (weight, height, BMI), and efficacy variables at Baseline I will be summarised.

Past and concurrent medical, neurological, and psychiatric disorders at the lead-in study Screening Visit (coded using the Medical Dictionary for Regulatory Activities [MedDRA], Version 19.0 or later), will be summarised.

The summaries will also be presented by lead-in study for the APTS.

LU Study Number: 14861B Trial Site Number: Study Level Pluto ID: CLI 00933680

8 Recent and Concomitant Medication

Recent and concomitant medication will be coded using the WHO Drug Dictionary (WHO-DDE), version WHO ATC MAR16., and summarised by anatomical therapeutic chemical (ATC) code, and generic drug name.

For the open label treatment period summaries will be prepared for:

- Concomitant medication continued after Baseline II
- concomitant medication started after Baseline II and at or before Baseline III for patients in APES2

For the open label treatment period with memantine summaries will be prepared for;

- concomitant medication continued after Baseline III
- concomitant medication started after Baseline III

A listing will be created that includes information about memantine dosages over the course of the open label treatment period with memantine.

9 Exposure

Exposure to IMP in this study will be defined as: date of last dose of IMP – date of first dose of IMP + 1

For details about handling of missing IMP start or stop date, see section 18.4.1 (IMP start and stop date)

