Exposure to IMP in each treatment period will be summarised using descriptive statistics, and include the patient years of exposure (PYE). PYE will be calculated as the sum of the number of days of exposure to IMP for each patient, divided by 365.25 days.

In addition, exposure to IMP in each treatment period will be categorised into day intervals. The intervals for the open-label treatment period are the following: $(1-28\ [0-1\ month], 29-56\ [1-2\ months], 57-84\ [2-3\ months], 85-126\ [3-4.5\ months], 127-168\ [4.5-6\ months], 169-252\ [6-9\ months].$ The intervals for the open-label treatment period with memantine are the following: $(1-168\ [0-6\ months], 169-252\ [6-9\ months], 253-364\ [9-12\ months], 365-448\ [12-15\ months])$. Missing values of exposure will not be imputed.

Number and percentage of patients with dose reduction of IMP to 30 mg/day in the open-label treatment period will be summarised. The mean dose of IMP will be calculated for each patient and summarised (mean, median, and lower and upper quartiles). Categorical summaries of patients' dosage at each visit will be presented as well.

LU Study Number: 14861B Trial Site Number: Study Level Pluto ID: CLI 00933680

10 Efficacy

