11.1.5 All Adverse Events

All adverse events will be listed for the APES and APES2.

An overview of the PYE, numbers, and percentages of patients with TEAEs, serious adverse events (SAEs), adverse events leading to withdrawal, or patients who died will be provided. For TEAEs, SAEs, and adverse events leading to withdrawal, the total number of events will be included.

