18.4.2 Withdrawal Date

For withdrawn patients with a missing Withdrawal Visit, the date of the last attended visit in the corresponding Treatment Period will be used in the calculation of time to withdrawal from treatment.

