18.4.4 Adverse Event Start and Stop Dates

If a stop date is missing due to an adverse event being on-going, the last visit date will be used as the stop date in the classification of TEAEs.

An adverse event with a missing or incomplete start or stop date will be classified as a pretreatment adverse event if the patient was taking placebo in the lead-in study and the following conditions are met:

- The start date is missing or incomplete, and the stop date is prior to the Baseline II visit, or the stop date is incomplete but known to be prior to the Baseline II visit (stop day is missing and stop year and month are before the year and month of the Baseline II visit, or stop day and month are missing and stop year is before the year of Baseline II)
- The start date is incomplete but known to be prior to the Baseline II visit (start day is missing and start year and month are before the year and month of the Baseline II visit, or start day and month are missing and start year is before the year of the Baseline II visit), and no change in intensity

If a start date is missing for an adverse event and the stop date is prior to the Baseline II visit, then the adverse event will be regarded as starting prior to the study and will not be included in the reporting of AEs in the study. In all other instances of an adverse event with a missing start or stop date, the adverse event will be classified as a TEAE.

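### A treated patient with a missing IMP stop date adds nothing to patient-years while their adverse events still count, so PYE can only be too low

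*SAP*

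**What the plan says.** SAP section 9 defines a patient's exposure as last dose date minus first dose date plus 1. It then states: "PYE will be calculated as the sum of the number of days of exposure to IMP for each patient, divided by 365.25 days". The same section says that missing exposure values are not imputed.

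SAP 18.4.1 treats the two ends of exposure differently. A missing start date is set to the Baseline II date. A missing stop date is left missing, and "the patient will contribute as having no exposure in the calculation of PYE". One exception follows: "If it can be ascertained from other data that the patient did take IMP until a specific date, this date may be used". No data source is named, and use of the exception is not required.

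The adverse event side does not depend on the stop date:

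- SAP section 4 defines the APTS by at least one dose of IMP, with no condition on a known stop date.
- SAP 11.1.3 and 11.1.4 define treatment-emergent events by onset or worsening after Baseline II. For patients who do not enter the memantine substudy, events count up to the last protocol-specified contact.
- SAP 11.1.5 puts both sides in one table: "An overview of the PYE, numbers, and percentages of patients with TEAEs", together with serious events, withdrawals due to adverse events, deaths and total event counts.

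**The concern.** PYE is a sum, so entering zero for a patient is the same as leaving that patient's time out. The difficulty is that the patient's events are not left out with it. The overview then sets events from all treated patients beside time from only those with a usable stop date.

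For an APTS patient the zero is known to be false, because section 9's formula gives at least 1 day once one dose has been taken. The error therefore has one direction: PYE too low, and any events-per-PYE figure too high. The table serves the primary objective, which is safety.

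The exception does not settle the matter. Because it is permissive and names no source, two analysts could both follow the SAP and report different PYE. Open-label tables are shown by lead-in treatment group (SAP section 5), so if missing dates were unevenly spread, the shortfall would differ between columns.

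**Working it through.** **Scale.** The plan's own figure reproduces: (3 × 310 + 3 × 280) × 0.85 × 0.85 = 1770 × 0.7225 = 1278.8, stated as about 1280 completers (SAP section 15). Lead-in completers number 1770 × 0.85 = 1504.5. This is an upper bound on entrants, since some completers will not be eligible.

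**Formula.** Let m be the share of treated patients whose stop date is missing and unresolved, d their mean true exposure in days, and D the mean true exposure of all treated patients.

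- Share of true PYE lost: L = m × d / D
- Inflation of any derived events/PYE: 1 / (1 − L)

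Neither m nor d is in the documents. The number of patients cancels out of L.

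**Illustration, open-label period.** Assume 1505 entrants, 85% with 196 days and 15% with 90 days.

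- D = 0.85 × 196 + 0.15 × 90 = 180.1 days
- True PYE = 1505 × 180.1 / 365.25 = 742.1
- m = 1%, d = 120: lost PYE = 1505 × 0.01 × 120 / 365.25 = 4.9; L = 0.67%; rate × 1.007
- m = 2%, d = 120: lost PYE = 9.9; L = 1.33%; rate × 1.014

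**Range.** Let r be the mean true exposure of affected patients relative to the others. The ratio of PYE under the SAP to true PYE is (1 − m) / (1 − m + m × r), and the rate factor is 1 + m × r / (1 − m).

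| m | r | PYE understated by | Derived rate multiplied by |
|---|---|---|---|
| 0.5% | 0.5 | 0.25% | 1.003 |
| 1% | 0.5 | 0.50% | 1.005 |
| 2% | 0.5 | 1.01% | 1.010 |
| 5% | 0.5 | 2.56% | 1.026 |
| 5% | 1 | 5.00% | 1.053 |
| 10% | 1 | 10.00% | 1.111 |

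The rows with r = 1 are upper cases. They assume that affected patients were treated for as long as everyone else.

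**Memantine period.** With 100 patients and 168 days, full PYE is 100 × 168 / 365.25 = 46.0. Each unresolved full-length patient costs 168 / 365.25 = 0.46 PYE, so five of them would leave 43.7. One qualification applies: SAP section 4 admits patients to APTS2 on a dose of IMP or memantine. The statement that zero is false therefore covers only those who took IMP in that period.

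**The case against.** The case against giving this much weight is substantial, and most of it stands.

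- **No planned result is a rate.** SAP 11.1.5 lists PYE, patient numbers, percentages and event totals. Percentages use patient counts. A reader might infer that the trial's reported adverse event rates will be overstated; the documents do not support that, because no exposure-adjusted rate is defined.
- **The exception may resolve most cases.** The protocol requires capsule counts and wallet-card return at each visit (6.4), patient-specific dispensing logs (6.6) and, in the substudy, recorded time of last dose with each PK sample (9.3). Zero applies only where no date is found or the option is not used.
- **Who is affected is not documented.** It is tempting to say that the missing dates will belong to patients who died or were lost to follow-up. That is plausible inference only. Such patients would also tend to have shorter exposure, which argues against the full-length scenarios.
- **The SAP is not plainly inconsistent with itself.** Section 9 also declines to impute exposure. The last-visit conventions elsewhere have other purposes: "the date of the last attended visit in the corresponding Treatment Period will be used" concerns time to withdrawal, and "the last visit date will be used as the stop date in the classification of TEAEs" concerns event classification. They show that a workable convention exists, not that 18.4.1 breaks a general rule.
- **The error cannot hide a signal.** It makes a derived rate look worse.
- **PYE is already an imperfect time at risk.** It ends at the last dose, while new serious events are collected for about 4 more weeks. For a completer outside the substudy that is 28 / 196, about 14% of treatment time, which is larger than the 0.7% to 1.3% illustrated here.

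These points limit the consequence. They do not make zero a correct value, and they do not make a permissive sentence into a rule.

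**Conclusion.** The defect is real and its direction is certain: following SAP 18.4.1 as written gives a PYE that can only be too low whenever a treated patient's stop date stays unresolved. Any rate derived from the overview is then too high. Planned percentages and event counts do not change.

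The size cannot be fixed from the documents. On the stated assumptions it is about 0.7% to 1.3% of PYE at 1% to 2% unresolved dates and 120 days of true exposure. It would reach several percent only if unresolved dates were common. This is a rule worth correcting because it is wrong and cheap to replace. It is not a threat to the trial's safety conclusions.

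**What to change.** In SAP 18.4.1:

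- Delete the zero-exposure clause.
- State that a missing IMP stop date will be replaced by the last date on which intake is supported by dosing or drug-accountability records. If there is none, it will be replaced by the last attended visit in that treatment period, the convention already used in 18.4.2.
- In either case the date is never later than the recorded withdrawal date or the date of death.
- Report the number of patients with an imputed or unresolved date, and give PYE with and without them.

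In SAP section 9, amend the sentence on missing exposure so that it does not contradict the new rule.

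The cost is a few sentences and a few lines of programming. The downside is that a visit date is only a proxy for the last dose and can misstate exposure by up to a visit interval in a few patients. That is 8 weeks between Visits 4, 5 and 6 (days 84, 140 and 196), and in the substudy 12 weeks between Visits 10 and 11 (days 280 and 364). Where dosing stopped before that visit, exposure would be overstated and a derived rate would look too low. Reporting PYE both ways shows how much this matters.

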18.4.2 Withdrawal Date

For withdrawn patients with a missing Withdrawal Visit, the date of the last attended visit in the corresponding Treatment Period will be used in the calculation of time to withdrawal from treatment.

18.4.3 Medical Disorder Start and Stop Dates

No imputation of dates will be done.

LU Study Number: 14861B Trial Site Number: Study Level Pluto ID: CLI 00933680

18.4.4 Adverse Event Start and Stop Dates

If a stop date is missing due to an adverse event being on-going, the last visit date will be used as the stop date in the classification of TEAEs.

An adverse event with a missing or incomplete start or stop date will be classified as a pretreatment adverse event if the patient was taking placebo in the lead-in study and the following conditions are met:

- The start date is missing or incomplete, and the stop date is prior to the Baseline II visit, or the stop date is incomplete but known to be prior to the Baseline II visit (stop day is missing and stop year and month are before the year and month of the Baseline II visit, or stop day and month are missing and stop year is before the year of Baseline II)
- The start date is incomplete but known to be prior to the Baseline II visit (start day is missing and start year and month are before the year and month of the Baseline II visit, or start day and month are missing and start year is before the year of the Baseline II visit), and no change in intensity

If a start date is missing for an adverse event and the stop date is prior to the Baseline II visit, then the adverse event will be regarded as starting prior to the study and will not be included in the reporting of AEs in the study. In all other instances of an adverse event with a missing start or stop date, the adverse event will be classified as a TEAE.

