11.1.3 Classification of Adverse Events

Adverse events will be classified according to the time of onset of the adverse event: treatment-emergent adverse event (TEAE) – an adverse event that starts or increases in intensity after the date of Baseline II.

An adverse event is considered causally related to the use of the IMP when the causality assessment by the investigator is *probable* or *possible*.

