11.1.4 Allocation of TEAEs to Treatment Periods

TEAEs will be allocated to treatment periods according to the time of onset of the adverse event:

• *adverse event in the open-label treatment period* – an adverse event that starts or increases in intensity after the date of Baseline II and at or before the date of the last protocol-

LU Study Number: 14861B Trial Site Number: Study Level Pluto ID: CLI 00933680

- specified contact in the study for patients not continuing into the open-label treatment period with memantine, and at or before the date of Baseline III for patients in the APES2.
- adverse event in the open-label treatment period with memantine an adverse event that starts or increases in intensity after the date of Baseline III and at or before the date of the last protocol-specified contact in the study.

Note, the completion Visit in the lead-in studies are the same as the Baseline II Visit in the extension study, and adverse events ongoing or starting at Baseline II and not increasing intensity will only be reported in the lead-in study.

All tables and listings will be presented separately for adverse events in the open label treatment period, and the open label treatment period with memantine.

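### SAP 18.4.4 ties its pretreatment class to lead-in placebo, so an AE with an incomplete start date known to precede Baseline II and no stop date can be a TEAE in former idalopirdine patients only

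*SAP*

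**What the plan says.** SAP 11.1.3 defines a TEAE as "an adverse event that starts or increases in intensity after the date of Baseline II". SAP 11.1.4 adds that "adverse events ongoing or starting at Baseline II and not increasing intensity will only be reported in the lead-in study". Neither depends on the lead-in arm. Nor does protocol 16.9.1, which counts from the first extension dose.

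SAP 18.4.4 handles missing and incomplete dates in four steps:

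1. For an on-going event, the last visit date serves as the stop date when TEAEs are classified.
2. An event with a missing or incomplete date "will be classified as a pretreatment adverse event if the patient was taking placebo in the lead-in study and the following conditions are met". Two bullets follow. The first begins "The start date is missing or incomplete, and the stop date is prior to the Baseline II visit" and also accepts a partial stop date known to be earlier. The second begins "The start date is incomplete but known to be prior to the Baseline II visit" and requires no change in intensity.
3. For every arm: "If a start date is missing for an adverse event and the stop date is prior to the Baseline II visit", the event is left out of the study's AE reporting.
4. The closing sentence: "In all other instances of an adverse event with a missing start or stop date, the adverse event will be classified as a TEAE".

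SAP section 17, which lists changes from the protocol's analyses, mentions only the C-SSRS.

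**The concern.** Whether an event began before or after Baseline II is a matter of dates, yet step 2 makes the answer depend also on lead-in treatment. An event whose known month or year puts its onset before Baseline II can leave the TEAE count if the patient had placebo. For a former idalopirdine patient no such exit is written, and the closing sentence may claim the event.

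TEAE tables serve the primary safety objective, and SAP section 5 presents the open-label tables by lead-in treatment group. An arm-dependent rule therefore enters the displayed columns directly. It would also report again, in the extension, events that 11.1.4 assigns to the lead-in study alone.

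**Working it through.** The plan gives no figure on this point, so the check applies the rule to every combination of start and stop date.

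**Inputs.** Events with no later change in intensity. Start date: complete on or before Baseline II; incomplete but known to be before it; incomplete and not placeable; missing. Stop date: complete before; incomplete but known before; complete after; on-going; incomplete and not placeable; missing and not on-going. Each combination is classified by 18.4.4, and by 11.1.3 where 18.4.4 is silent.

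**Which patterns matter.** Combinations that place the event on or before Baseline II: 6 (complete start) + 6 (incomplete, known before) + 2 (not placeable, but stop before) + 2 (missing, but stop before) = 16. Of these, 4 start types × 2 stop types = 8 have a stop before Baseline II. They should be rare, because footnote j to protocol Panel 2 transfers only AEs on-going at lead-in Visit 7. That leaves 16 − 8 = 8.

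**Readings.** *Strict*: *missing* in the closing sentence means wholly absent. *Broad*: it also covers *incomplete*. The table takes the bullets as alternatives; each cell gives former placebo / former idalopirdine, and 'non' means not a TEAE. Under 11.1.3 and 11.1.4 every cell should be non / non.

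| Start date | Stop date | Strict | Broad |
|---|---|---|---|
| Complete, on or before Baseline II | Complete, after | non / non | non / non |
| Complete, on or before | On-going (last visit date used) | non / non | non / non |
| Complete, on or before | Incomplete, not placeable | non / non | TEAE / TEAE |
| Complete, on or before | Missing, not on-going | TEAE / TEAE | TEAE / TEAE |
| Incomplete, known before | Complete, after | non / non | non / TEAE |
| Incomplete, known before | On-going (last visit date used) | non / non | non / TEAE |
| Incomplete, known before | Incomplete, not placeable | non / non | non / TEAE |
| Incomplete, known before | Missing, not on-going | non / TEAE | non / TEAE |

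**Arm differences.** One of 8 on the strict reading and 4 of 8 on the broad one. Each runs the same way: TEAE after idalopirdine, not after placebo.

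**Bullets joint.** The first bullet needs a stop before Baseline II, so none of the 8 patterns meets both. Placebo patients then get the idalopirdine result in the last four rows, and the arms differ in 0 of 8. The conflict with 11.1.3 does not go away: the last row becomes a TEAE in every arm.

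**Error common to all arms.** The fourth row does not depend on arm. Both bullets need a missing or incomplete start, so a complete start before Baseline II with a missing, not on-going stop reaches the closing sentence in every arm and becomes a TEAE, contrary to 11.1.3.

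**The eight patterns set aside.** If such records exist, the counts over all 16, with the bullets as alternatives, are 2 (strict) and 9 (broad). They fall to 1 and 8 if the exclusion in step 3 also accepts a partial stop date. With the bullets joint they are 0 and 2.

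These are counts of patterns, not frequencies of records.

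**The case against.** **The strict reading fits the text better.** Section 18.4.4 uses *missing* and *incomplete* as different words, and the closing sentence uses only *missing*. This stands. An incomplete start known to precede Baseline II with a recorded or on-going stop then falls back to 11.1.3 and 11.1.4 and is not a TEAE in any arm.

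**The usual transferred event is already handled.** Footnote j brings in on-going events, and the first sentence of 18.4.4 gives them a stop date. This also stands on the strict reading. What remains is a stop date that is missing without the event being on-going. That should be uncommon: protocol 10.3 asks for start and stop dates, and protocol 8.5 has non-serious events still open at follow-up recorded as on-going.

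**The bullets might be joint.** The text does not say. A joint reading would leave the word *missing* in the first bullet without effect, because the second bullet needs an incomplete start. Alternatives are therefore likelier, but this is an inference.

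**The label *pretreatment* cannot describe patients already on idalopirdine.** Correct: protocol 10.1.1 reserves it for events before the first IMP dose, which may explain the condition. It justifies a different label, not TEAE status.

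**Over-counting TEAEs is conservative.** That is reasonable for the total column and for dates that cannot be placed. It does not support a rule that varies by arm when the date can be placed.

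A reader might infer that any incompletely dated event known to precede Baseline II escapes TEAE status only in former placebo patients, so that on-going lead-in events generally become extension TEAEs after idalopirdine. The documents do not support that. A missing start with a stop before Baseline II is excluded in every arm, and the on-going case differs by arm only on the broad reading.

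**Conclusion.** The point holds in a limited form and is minor. Section 18.4.4 makes a non-TEAE class depend on lead-in placebo, gives former idalopirdine patients no counterpart, and so departs from 11.1.3 and 11.1.4 without declaring it in section 17.

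Among events not already ended before Baseline II, the arms are treated differently in one of eight date patterns if the bullets are alternatives and *missing* is strict, in four if *missing* includes *incomplete*, and in none if the bullets are joint. The first combination fits the text best. Any arm difference adds TEAEs to the former idalopirdine columns. The error with a complete early start and a missing, not on-going stop affects all arms alike and should not be described as arm bias.

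The number of affected records cannot be derived from the documents and is probably small. The tables are descriptive. The contradiction in the wording is certain; a material effect on the tables is not shown.

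**What to change.** In SAP 18.4.4:

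- Remove the placebo condition from the classification.
- State for all lead-in arms that an AE is not an extension TEAE, whatever its stop date, if its start date (complete, or incomplete with the known month or year settling the matter) is on or before Baseline II and its intensity does not later increase. Use *increase*, as 11.1.3 does, in place of *change*.
- Keep the first bullet's rule (start missing or incomplete, stop known to be before Baseline II) for all arms, and state that the two bullets are alternatives.
- Limit the closing TEAE sentence to events whose onset cannot be placed relative to Baseline II, for example when the day is missing and the month is that of Baseline II.

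Two additions are optional and not part of the error. A neutral label such as 'lead-in AE' would avoid calling events in former idalopirdine patients pretreatment. A matching rule for Baseline III would help, because 11.1.4 assigns to the memantine period an event that "starts or increases in intensity after the date of Baseline III" while 18.4.4 does not mention that visit.

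The cost is SAP wording and the AE classification code. No new data are needed.
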